Aim 1: Determine the impact of the *Compañeros en Salud* (Partners in Health) curriculum in conjunction with RT-CGM on glycemic control in Latinx patients with T2D. We will enroll 100 Latinx patients with uncontrolled T2D through a federally funded healthcare network across the Seattle region. Participants will be randomized to receive the *Compañeros en Salud* diabetes self-management education and support (DSMES) intervention with or without RT-CGM (n=50 per group) over 12 weeks with an additional 12 weeks of follow-up.(control= blinded -CGM+ Education and intervention= RT-CGM + education). Study visits will be held at screening, baseline(0-4 weeks) and 12 weeks (+/- 2 weeks) and 24 weeks (+/-2) weeks. Participants in the blinded -CGM+ Education group will undergo blinded CGM for 1 week at baseline and for 10 days after each study visit. The primary outcome will be A1C. Secondary outcomes will include time in range as measured by CGM and other CGM indices, body mass index, waist circumference, and systolic and diastolic blood pressure.

Aim 2: Engage key stakeholders to optimize acceptability and minimize barriers to participation in the intervention. After 25% of participants have completed the intervention, we will convene a committee of stakeholders that includes study participants (both completers and non-completers), community providers, diabetes educators, and patient navigators. Key barriers and facilitators to the intervention will be identified by stakeholders, and the intervention will be amended based on stakeholder feedback. The impact of these revisions on participant engagement during the study intervention will be analyzed.

Aim 3. Determine the effects of the *Compañeros en Salud* curriculum with or without adjunct RT-CGM on diabetes-related behaviors and distress. At baseline and 12-+2 weeks and 24 +/- 2 weeks, participants will complete surveys capturing dietary behaviors, physical activity, and diabetes-related distress. Participants will be provided with pedometers, and activity data will be captured for 10 days following each study visit. **Sub-aim 3A:** As an exploratory sub-aim, we will examine behavioral changes in other members of participants' households through brief surveys. This sub-aim will provide preliminary data regarding a possible "ripple effect," the capacity for an intervention in 1 individual to affect health-related behaviors in other household members.

B. Background

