Participant Recruitment: A maximum number of 120 eligible patients **will be** enrolled (with goal 100 completed) and randomized from Sea Mar health centers. The study will recruit from 6 primary care clinics (Des Moines Medical Clinic, White Center Medical Clinic, Federal Way Medical Clinic, Kent Medical Clinic, Seattle Medical Clinic, Burien Medical Clinic) given the high volume of Latinx populations who receive care at these sites. Additional participants may come from other Sea Mar clinics, and from community engagement or the University of Washington clinics. Patients will be referred by their local primary care providers or by Sea Mar health education team and their review of patients with uncontrolled diabetes or new diagnosis of diabetes in the Sea Mar health system record. Patients who express interest will be contacted by telephone, email and/or in person by on-site research coordinators to ascertain interest and confirm eligibility criteria. Eligible individuals will be scheduled for their screening visit, ideally within 2 weeks of the contact.

Recruitment will be quarterly with one Spanish and one English speaking 12-week curriculum with a goal of 20-35 participants per DSMES cycle. We anticipate a roughly even distribution between English and Spanish speaking participants (e.g., 10-20 participants per cohort per language-specific curriculum cycle). A total of 4-6 DSMES cycles will need to be completed to reach 100 participants.

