AIM 1: Our primary endpoint for Aim 1 is the change in A1C from baseline to 12+/-2 weeks (end of the intervention period). Secondary outcomes include between-group differences in change in A1C at

24+/-2 weeks and changes in body weight, BMI, and blood pressure at 12+/-2 and 24+/-2 weeks. We will use simple descriptive statistics to quantify between-group differences in changes in CGM indices including TIR, mean glucose, mean amplitude of glycemic excursions, TAR, TBR, and coefficient of variation. The primary outcome of A1C will be assessed using a random-intercept random-slope linear mixed effects regression model that adjusts for an indicator of RT-CGM and time (baseline, visit 2, and visit 3) as fixed effects. To assess the effectiveness of the *Compañeros en Salud* curriculum, inference for Aim 1 will focus on the change in A1C from baseline to 12 weeks for the entire cohort (regardless of RT-CGM status). Secondary outcome measures of TIR, body mass index, waist circumference, and systolic/diastolic blood pressure will be similarly assessed using a generalized linear mixed effects model appropriate for each type of outcome measurement.

We will conduct a missing data analysis to describe and characterize enrolled participants who do not provide data due to attrition. Linear mixed effects models naturally handle intermittent missing data through maximum likelihood estimation. As described by Molenberghs and Kenward,⁴⁹ we will use inverse probability weighting in secondary analysis within each longitudinal regression model to inflate the weights of cases that are underrepresented in the analysis due to selective attrition and/or non-participation. We will also conduct sensitivity analyses using 10-fold multiple imputation to assess the robustness of the results when missing data are imputed. The characteristics of non-responders will be summarized in our final report, and we will present the sensitivity of the estimated treatment effect due to alternative missing data methods

Aim 2: For this Aim, the primary outcome will be the difference in % of DSMES education sessions attended for participants who complete the study before and after the stakeholder convening. Additional endpoints will similarly assess the differences in the following metrics of participant engagement: % adherence to RT-CGM use, % of participants who complete all study visits, and % of eligible patients who enroll in the study.

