N: Glucose/CGM Data /Evaluation Measures: For participants in both the education-only and RT-CGM study arms, the % time the CGM device was worn over each period of use will be captured. Glycemic outcome measures include time in range (TIR), mean glucose, coefficient of variation, mean amplitude of glucose excursion (MAGE), % time below range (TBR) (<70 mg/dL), and % time above range (TAR) (>180 mg/dL). Between-group comparisons for CGM-derived glycemic metrics will be assessed based on changes from baseline to study week 12 and baseline to study week 24.

O. Advisory Board: We will convene key stakeholders in an advisory board after approximately 20-25% of participants have completed the 12-week intervention and again during years 2 and 3 of the study. The first convening will occur after 1 education cycle has been completed for both an English- and Spanish-speaking cohort, with an estimated 20-30 participants having undergone the intervention. Key stakeholders will meet specifically to address barriers to entering and completing the education intervention, implementing the behavioral changes recommended by the DSMES curriculum, and adhering to CGM use in the RT-CGM arm of the study. Accordingly, invited stakeholders will include patients who were eligible but opted against participation, participants who enrolled but did not complete the intervention phase of the study, participants who completed the 12-week intervention, and participant's household member if desires. Additional stakeholders are described below. The board will be asked to assess possible barriers to participant engagement, including the following: support for technology use, adequacy of RT-CGM training, food insecurity, safety concerns, and time commitment and sustainability.

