Revisions to the study protocol that enhance access and engagement will be implemented for the remainder of the study period, and indices of engagement (% of eligible participants who enroll, % of education sessions attended, % of participants who complete all study procedures, % adherence to CGM use) will be measured prior to and after the changes implemented consequent to the stakeholder convening. Key stakeholders will be convened again in years 2 and 3 of the project. These meetings also will focus on barriers to sustaining the intervention, particularly with regard to the availability of essential resources (CGM devices; CDEs, health educations, PN, and other personnel; infrastructure to support remote education sessions, etc.) and therefore will be key for the design of future interventions.

Key stakeholders:

The advisory board will be chaired by [name], MD, Director of the UW Medicine Diabetes Institute LatinX Diabetes Clinic. Other members will include PN and members of Ventanillas de Salud (a local chapter with the Mexican consulate that works to combat health disparities). In addition, Spanish-speaking diabetes educators, primary care providers, and a quality improvement officer from Sea Mar will be included in the board. Ten participants from the first two cohorts (5 from each cohort of participants (with the goal to include 2 participants who withdrew from the intervention). We will ask

the first 3 participants who enrolled and completed greater than 70% of the sessions to be on the board. We will also ask the first 2 participants who stopped going to the sessions to be on the advisory board. If they decline we will continue to ask the next participant enrolled until we have 3 participants who have engaged in the educational sessions and 2 participants who stopped attending the sessions.

We hope to improve the diabetes classes and discuss any challenges people may be having with participating in the diabetes classes, and challenges with telemedicine sessions. We will ask questions either in a group setting or 1:1 tele-health interview about living with diabetes and any barriers/difficulties they are experiencing. Interviews will last approximately 50-60 minutes and will be recorded in order to ensure all answers are transcribed and then collated in a de-identified manner for QI for the program

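### Aim 2 promises the impact of the stakeholder revisions, but its uncontrolled before/after contrast against the first education cycle cannot separate the revisions from calendar time

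*Combined protocol and SAP*

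**What the plan says.** The opening aims section sets the goal of Aim 2: "The impact of these revisions on participant engagement during the study intervention will be analyzed".

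Section E (Data Analysis Plan, Aim 2) defines the primary outcome as "the difference in % of DSMES education sessions attended for participants who complete the study before and after the stakeholder convening". Three other engagement measures are handled in the same way: adherence to RT-CGM, completion of all visits, and enrollment among eligible patients.

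Section O (Advisory Board) fixes the timing: "The first convening will occur after 1 education cycle has been completed for both an English- and Spanish-speaking cohort, with an estimated 20-30 participants" having been through the program. It also places the meeting "after approximately 20-25% of participants have completed the 12-week intervention". The resulting revisions then hold for all remaining participants, and the engagement measures are compared before and after the changes. The same section adds: "Key stakeholders will be convened again in years 2 and 3 of the project".

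On recruitment, section D names six clinics and then allows for more: "Additional participants may come from other Sea Mar clinics, and from community engagement or the University of Washington clinics". It expects 4-6 cycles in total, each with one English and one Spanish class.

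**The concern.** The aim is worded causally, but the planned contrast is historical. Its comparator is, by design, the first cycle delivered. No later cycle runs without the revisions. Both arms receive them, so randomization gives Aim 2 no protection. The Aim 2 analysis text names no control group, cycle or calendar-time term, covariate or caveat on interpretation. The mixed models in section E are written for Aims 1 and 3.

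At stake is the conclusion drawn from this aim's primary outcome. A rise in attendance could be reported as the effect of engaging stakeholders when it reflects a program settling in. A flat result could equally hide a real benefit offset by a downward trend.

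**Working it through.** **1. What the estimate contains.** Let R be the true effect of the revisions and D the change in attendance that would have occurred without them (start-up, trend, case mix). Then

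expected (after minus before) = R + D.

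Every before participant is unrevised and early, and every after participant is revised and late. The data give only the sum. No covariate or model separates R from D, because no cycle is late and unrevised, or early and revised.

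**2. Inputs from the documents.** Total 100 participants and 15% attrition (section E, Sample Size Estimation); first convening after one cycle in each language, 20-30 participants (section O); 4-6 cycles of two classes (section D). That makes 2 classes before and 8 - 2 = 6 to 12 - 2 = 10 classes after. Section E states a two-sided 5% error rate for its power calculations. For Aim 2 it gives no SD, effect size, power or test, so there is no plan figure to reproduce.

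**3. Assumptions, not in the documents.** Split of 25 before and 75 after; SD of individual attendance 30 percentage points (range 25-35); R = 0; D of 5, 10 or 15 points; a two-sample normal test at two-sided 5%.

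**4. Formulas.** SE = SD × √(1/25 + 1/75), and the probability of significance = Φ(D/SE - 1.96) + Φ(-D/SE - 1.96).

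| SD | SE | D = 5 | D = 10 | D = 15 |
|---|---|---|---|---|
| 25 | 5.8 | 14% | 41% | 74% |
| 30 | 6.9 | 11% | 30% | 58% |
| 35 | 8.1 | 9% | 24% | 46% |

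With D = 0 the figure is 5%.

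**5. With attrition.** The contrast is among completers. At 85% retention, 25 and 75 become about 21 and 64. At SD 30, SE = 30 × √(1/21 + 1/64) = 7.5, and a 10-point drift is significant 26% of the time (36% at SD 25, 21% at SD 35).

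**6. Case mix alone.** If 40% of later participants came from a source whose attendance differed by 20 points (both figures assumed), the apparent change would be 0.40 × 20 = 8 points with no revision effect.

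**7. Where the split falls.** Section E divides at the convening, while section O divides at the changes that follow it. With quarterly recruitment and 12-week classes, a second cycle could be under way between the two. Its classification is not settled.

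**The case against.** The strongest reply is that the operative text already speaks of a difference and of measurement before and after. It states no Aim 2 test, threshold or decision rule. On that view only one word in the aims section overreaches. That is fair as to size: the remedy is mostly wording. But that word states what the aim is meant to deliver, and nothing in section E tempers it.

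Several stronger readings are tempting and are not supported:

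- **That staff, navigators and the Zoom set-up are new in the first cycle, so later attendance must rise.** No section says so. The curriculum was piloted in Seattle, sessions are scripted, staff training is scheduled, and navigators check devices beforehand. Drift could also run downward, for instance if the most motivated patients enroll first.
- **That recruitment sources will shift.** Section D permits further sources but gives no plan or date for a change. It is a possible threat, not an expected one.
- **That the after period will mix several sets of revisions.** Section O schedules later meetings but ties them mainly to sustaining the program and designing future work. It does not say that they will change the protocol again.
- **That omitting arm and language is a serious confounder.** Each cycle has a class in both languages, the first convening waits for both, and arm is assigned in small permuted blocks. Both should stay near balance over time.

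The numerical illustration also depends on an assumed SD, an assumed drift and a test that the plan does not specify. The identification argument in step 1 of the working depends on none of these.

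**Conclusion.** The point stands in limited form. The Aim 2 comparison can describe how attendance differed between the first cycle and later ones, but it cannot attribute that difference to the stakeholder revisions. This follows from the design alone: one early unrevised period, universal roll-out afterwards, and no concurrent comparison. The bias equals whatever drift occurs, in either direction. The documents establish neither its sign nor its size.

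The figures of about 30% (24-41%) for a 10-point drift, or about 26% with attrition, show only that a moderate drift could plausibly be mistaken for an effect. They are not a forecast. The randomized A1C comparison is not affected.

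**What to change.** In the aims section, replace the sentence that promises an impact analysis with a descriptive before/after comparison of engagement.

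In section E, Aim 2:

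- Report attendance for each cycle and class language.
- Classify each cycle by whether the revisions were actually in force, with the date recorded. This settles the mismatch between the convening (section E) and the changes (section O).
- Show any later revisions separately, if they occur.
- State that the effect of the revisions cannot be separated from start-up and calendar-time effects.

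Adjustment for recruitment source is optional, and possible only if source is recorded, which the documents do not confirm. It would not remove the confounding. Nor would judging the first cycle against the spread of the 3-5 later cycles, since all of those may be revised.

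The cost is a wording change, one table and a dated record of revisions, with no change to trial conduct. The downside is that Aim 2 can claim less.

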Participants will receive a telephone and or text and or email reminder 24 hours before each scheduled intervention class. Participants will send their name and may only use their first name or pseudonym if preferred through the chat feature on Zoom to track attendance. At the conclusion of each class, participants will be asked to set a goal related to the presented topic and will complete a brief satisfaction questionnaire. At each subsequent class, the facilitator will ask participants to discuss their successes and challenges in achieving their goals. For participants who miss a class, study staff will make up to 2 telephone calls to check in and confirm attendance for the next session. If 3 or more people miss a class, the facilitator will try to schedule a make-up class before the next scheduled session. If fewer than 3 people miss the class, or if it is not possible to schedule a make-up session, materials for the missed class will be available as recording but live attendance via Zoom will be stressed. People who miss 4 consecutive classes or a total of 8 total classes will be considered dropouts. However, these participants will not be turned away from future sessions if they decide to attend. All participants will always be included in follow-up data collection, regardless of class attendance or retention.

H. Study Design

Screening: Interested volunteers will be pre-screened by telephone or in person in respective clinics or via televisit and then scheduled for a screening visit (week 0). If potential participants express interest, they will be provided an email address or phone number to call for more information.

Alternatively, participants will be asked if they would like to be called to receive more information and are willing to provide their contact information to study staff. If after receiving more information, the potential participant is interested, then pre-screening questions (appendix C) will be asked. If still eligible, then a screening appointment will be arranged by study staff. If the participant is not interested in participating, the participant will continue standard diabetes care with their primary care clinic .

Study visits and intervention:

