Baseline Visit/Visit 1. Base line visit is 2-4 weeks prior to Week 1, which is the start of education intervention. Week 1 is the first week of the education sessions. Baseline visit will occur in the participant's home or at a local Sea Mar clinic and/ or maybe a combination of remote and in-person. A research coordinator will review the full informed consent document, explaining study goals, procedures, and any potential risks in Spanish or English. Consent (appendix Z ?) will be obtained prior to any screening procedures being completed, and conducted in a quiet room or private televisit. Participant will be given ample time to ask questions, and a copy of the signed consent form will be given prior to start of screening visit procedures. Participants will fill out a contact form, including emergency contact (appendix Z1). Study staff will review medical history and medications and family history (appendix D), as well as all inclusion/exclusion criteria. Point of care A1C will be measured via point of care testing with a Siemens DCA Vantage A1C Analyzer, at LabCorp or quest for serum A1C if remote visit is completed. All women of child-bearing potential will undergo a urine pregnancy test either point of care or at LabCorp. Participants who meet criteria for enrollment and wish to proceed with study participation will be randomized to an intervention arm in unblinded fashion.

Remote Consent : If baseline visit is remote/virtual, the consent form will be sent to the participant via REDCap to be viewed and signed remotely. Subjects can also request that a paper copy of the consent be mailed to them before Visit 1. The informed consent discussion includes time for the potential participant to read over the consent form and to think about their questions. If the potential participant has questions outside of the Research Coordinator's scope, the potential participant will be offered a follow-up consultation with the Principal Investigator or Co-Investigator who can provide more information. As this is a minimal risk study, we will request a waiver of documentation of consent.

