Randomization. The study biostatistician will generate a randomized sequence of treatment group assignments using stratified permuted-block randomization (random block sizes of 2, 4, 6) stratified by A1C >9.0% and ≤9.0%. Sequences will be stored at and delivered through the REDCAP study database at the UW. Research staff will obtain the next randomization once a potential study participant has been determined to be eligible and has signed the study consent form.

Vital signs, anthropometrics measurements, and demographic information will be collected, and participants will be asked to complete study surveys as further detailed below. Participants will be asked to use pedometers and keep them on their person as much as possible during waking hours. Baseline data will be collected no more than 3 weeks prior to the initiation of the DSMES curriculum, and pedometer data will be collected over 10 days immediately following the baseline study visit. Both groups will undergo blinded CGM with insertion by study personnel over the same 10 days following the baseline visit. Participants will then have a follow up visit from a Patient Navigator 10-14 days after the initial visit (detailed below) If less than 72 hours of CGM data is obtained at follow up PN visit participants will be asked to repeat blinded CGM. Participants will be asked to continue their customary dietary and exercise habits until initiation of the intervention

Follow-up study visits given in a community setting will be within an acceptable window for data collection and held at weeks 12+/-2 weeks and 24+/-2 weeks (Visits 2: end of education intervention and visit 3:12 weeks after education intervention. The same procedures will be completed as described in detail below. Visits 2 and 3 also may be held in the participant's home or Sea Mar clinic according to the participant's preference and be completed through a remote RC visit with a PN in person visit to complete blood pressure, weight circumference and weight and A1c. The study team will continue to contact withdrawn participants to conduct an interview regarding barriers to study engagement.

Study Procedures

The following procedures will be performed at baseline (visit 1), (Visit 2) and (Visit 3):

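### The 12 ± 2 week window lets the primary end-of-intervention A1C be taken before the last classes and before the final RT-CGM wear

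*Combined protocol and SAP*

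**What the plan says.** - **Endpoint (Section E, Data Analysis Plan, Aim 1).** The primary endpoint is "change in A1C from baseline to 12+/-2 weeks (end of the intervention period". The mixed model takes time as three nominal visits (baseline, visit 2, visit 3). No use of actual visit dates is described.
- **Follow-up visits (Section H).** Visits at 12 ± 2 and 24 ± 2 weeks are labelled "Visits 2: end of education intervention and visit 3:12 weeks after education intervention".
- **Week 1 (Section H, Baseline Visit).** "Week 1 is the first week of the education sessions".
- **Week 0 (Section H, Screening).** Volunteers are pre-screened and "then scheduled for a screening visit (week 0".
- **Gap from baseline to the first class.** Section H first says "Base line visit is 2-4 weeks prior to Week 1, which is the start of education intervention". Later it says "Baseline data will be collected no more than 3 weeks prior to the initiation of the DSMES curriculum". The opening statement of Aim 1 says "Study visits will be held at screening, baseline(0-4 weeks) and 12 weeks (+/- 2 weeks" and names no zero point.
- **Curriculum (Section G).** Twelve weekly classes.
- **RT-CGM (Section H and the note under Figure 1).** Five 10-day wears are planned, the last starting on the day of the final class.

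**The concern.** The authors clearly intend visit 2 to show the result of the completed curriculum. A window symmetric about week 12 does not secure that, because the curriculum itself finishes in week 12: the early half of the window lies inside the intervention. No sentence orders the final class before visit 2, and the plan never states which zero point the 12 weeks use.

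Three results depend on visit 2: the whole-cohort A1C change (the primary analysis), the 12-week RT-CGM contrast, and the Aim 3 surveys. Values taken early would be reported as end-of-intervention values. The model would pool participants who had been offered different numbers of classes, with the difference due only to scheduling.

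In the RT-CGM arm, a visit before the final class follows at most four of the five wears, that is 4 × 10 = 40 days. The Preliminary Studies section cites the group's earlier trial as showing the best sustained A1C result with more than 48 days of use.

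**Working it through.** **The plan's own figure.** The SD of change is √(1.2² + 1.0² − 2 × 0.5 × 1.2 × 1.0) = √1.24 = 1.114. With n = 85 the standard error is 1.114/√85 = 0.121. For a 0.4 reduction, power = Φ(0.4/0.121 − 1.96) ≈ 0.91 (0.906 with the noncentral t). The stated 90% reproduces and is not in dispute.

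**Reading 1: weeks counted from the first class.** Class k falls on day 7(k − 1), so class 12 is on day 77, in study week 12.

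| Visit 2 in study week | Classes held by end of that week | Outstanding |
|---|---|---|
| 10 | 10 | 2 |
| 11 | 11 | 1 |
| 12 to 14 | 12 | 0 |

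The final RT-CGM wear runs from day 77 to day 77 + 10 = 87. A visit in week 12 (days 77 to 83) can therefore follow the last class but still precede the end of device use.

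**Reading 2: weeks counted from baseline.** With a gap of g weeks to the first class, class 12 falls g + 11 weeks after baseline. Classes held by week v are min(12, v − g + 1).

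| Gap | Class 12 at | Held at 10 wk | Held at 12 wk | Held at 14 wk |
|---|---|---|---|---|
| 2 wk | 13 wk | 9 | 11 | 12 |
| 3 wk | 14 wk | 8 | 10 | 12 |
| 4 wk | 15 wk | 7 | 9 | 11 |

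For any gap of 2 to 4 weeks, a visit at exactly 12 weeks precedes class 12. With a 4-week gap, the whole window does.

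**Which reading fits better.** On Reading 1, week 24 is 24 − 12 = 12 weeks after the curriculum's last week, as Section H says of visit 3. On Reading 2, visit 3 at 24 weeks would fall 24 − 15 = 9 to 24 − 13 = 11 weeks after class 12, which does not match. The blinded-CGM paragraph in Section H also places visit 2 at the end of education and baseline 2 to 4 weeks before education starts. Reading 1 is favoured.

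**Illustrative size under Reading 1.** Two assumptions are not in the documents: visit 2 is uniform over days 70 to 98 (10 to 14 elapsed weeks), and the A1C effect grows linearly to day 84.
- Share before class 12: (77 − 70)/(98 − 70) = 25%.
- Effect stops growing at day 84: half the visits average 77/84 = 0.917 of the full effect and half have all of it. The mean is 0.958, a loss of about 4%. On the 0.8-point improvement in Preliminary Studies, that is 0.77.
- Effect keeps growing at the same rate: the mean is 84/84 = 1.0, a loss of 0%.

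These figures use elapsed days. Reading the window as study weeks 10 to 14 starts it a week earlier, on day 63, and would make the loss somewhat larger.

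**The case against.** The strongest reply is that the intent is plain. Section H ties visit 2 to the end of education and starts Week 1 at the first class, so coordinators would aim for the end of the curriculum and few visits would fall in weeks 10 or 11. Both arms attend the same classes under the same windows, so the scheduling favours neither arm. The 4% loss also depends on stopping the effect at day 84. Section L describes A1C as reflecting about the last three months, so some gain after the last class is plausible and late visits could offset early ones. All of this stands, and it limits the size of the problem. It does not supply the missing rule: weeks 10 and 11 remain in window.

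A reader might infer something stronger: that follow-up is counted from screening, so that nearly everyone is measured mid-curriculum. With a uniform lead of 14 to 28 days, that count would put 94% of visits before class 12 and cut an assumed 0.8-point effect to 0.60, a 25% loss. With the 3-week limit in Section H (lead 14 to 21 days), it gives 87.5% and 0.63. The documents do not support this as the plan's meaning. Only the parenthesis in "scheduled for a screening visit (week 0" sets week 0 at screening. It says nothing about follow-up windows, and the rest of Section H points to the first class.

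**Conclusion.** The point holds as an inconsistency between label and window. On the best-supported count, weeks 10 and 11 are in window with two or one of the 12 classes outstanding and the final RT-CGM wear not begun. This follows from the text alone. The baseline count remains open because the endpoint is worded as running from baseline to 12 ± 2 weeks and Section H labels screening as week 0. It should be closed off, not treated as what the plan means.

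Neither the number of participants affected nor the A1C attenuation can be derived from the documents. From the first class, attenuation is probably small: about 0 to 4% under uniform timing over days 70 to 98 and linear growth. A reader should not infer a bias towards either arm, since scheduling is the same for both. Nor is the stated power refuted. The plan should be corrected because the primary endpoint should measure what its label says, and the correction is cheap.

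**What to change.** 1. State that follow-up weeks count from the cohort's first class, and that the week 0 label at screening does not set the visit windows.
2. Schedule visit 2 on or after the cohort's scheduled final class date, whether or not the participant attended. The window could be 0 to +2 weeks, or 0 to +4 weeks to keep the present four-week width. Set visit 3 at 12 ± 2 weeks after the same date, and reword the primary endpoint in Section E to match.
3. Say whether visit 2 in the RT-CGM arm is meant to fall during or after the final 10-day wear. That wear starts on the final class day, so either window could otherwise fall on both sides of its end.
4. Reconcile the three statements of the gap from baseline to the first class: 0 to 4 weeks, 2 to 4 weeks, and at most 3 weeks.

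The cost is protocol wording and a revised scheduling template, with no extra visits. The earlier scheduling weeks are given up, so visit 2 becomes either tighter (0 to +2) or somewhat later (0 to +4). In a trial that already allows for 15% attrition, the wider option may be easier to keep.
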